16.6. Safety

16.6.1. Analysis Population

The safety population is defined as all participants who receive at least 1 dose of study treatment in the extension study.

16.6.2. Methods of Analysis

16.6.2.1. Adverse Events

AEs will be coded using the Medical Dictionary for Regulatory Activities.

The incidence of all AEs, SAEs, deaths (all causes and ALS-related), and AEs leading to discontinuation will be summarized by system organ class and preferred term by treatment group. The incidence rate per person year may also be determined when long-term dosing follow-up is accrued. The AEs level of severity and relationship to study treatment will also be similarly summarized. For the summary of AEs by severity, if a participant has multiple events occurring in the same body system, then the event with the highest severity will be counted. The relationship to study treatment will be classified as related or not related.

16.6.2.2. Clinical Laboratory Results

Clinical laboratory evaluations include hematology, coagulation, blood chemistry, CSF assessments, and urinalysis. Laboratory data will be summarized using shift tables. The number and percentage of participants with shifts from baseline to high or low status for hematology, coagulation, blood chemistry, and CSF assessments and shifts from baseline to high or positive status for urinalysis will be presented by treatment group. In addition, summaries of the shift from baseline to the maximum postbaseline value and the shift from baseline to the minimum postbaseline value will be presented.

16.6.2.3. Vital Signs

Changes from baseline will be summarized for all vital signs by visit. A separate summary will be presented for incidence of clinically significant changes from baseline.

CONFIDENTIAL

The information contained herein may not be used, disclosed, or published without the written consent of
Biogen MA Inc.

16.6.2.4. Columbia Suicide Severity Rating Scale

C-SSRS data will be listed and summarized using descriptive statistics.

16.6.2.5. Limited Neurological Examinations

The changes from baseline in the limited neurological examination (coordination/cerebellar function, reflexes, and motor system) will be summarized by visit.

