4.9.4. ECG

The ECG test includes heart rate, PR interval, QRS interval, QT interval, QTc interval using Bazett's formula, QTc interval using Fridericia's formula, and RR interval.

Summary statistics for actual values and change from baseline in each ECG parameter will be presented by study group and visit.

The number and percentage of subjects with shifts from normal to each of the categorical values denoting an abnormal scan (abnormal not AE, abnormal AE) will be summarized by study group. A listing of subjects with abnormal status in ECG will be presented.

QTc (interval using Fridericia's formula) will also be examined to determine the incidence of clinically relevant abnormalities. The number of subjects evaluated and the number of subjects with clinically relevant abnormalities will be presented. The criteria for clinically relevant post-dosing abnormalities are:

- Maximum increase from baseline QTcF > 30 to 60 ms
- Maximum increase from baseline QTcF > 60 ms
- Maximum post-baseline QTcF > 480 to 500 ms
- Maximum post-baseline QTcF > 500 ms

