4.9.5. Mini-Mental State Exam (MMSE)

MMSE was collected based on earlier versions of 233AS102 Protocols and then removed from Protocol Amendment V6.0. All collected data will be still summarized for final analysis. Summary statistics for actual values and change from baseline of the total score of MMSE will be presented for each visit by study group. When there are multiple assessments during a single visit, the minimal value will be taken as the value for that visit. A listing of MMSE data for individual patients will also be provided.

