4.9.6. Limited neurological examinations

The number and percentages of the status in each assessment of coordination/cerebellar function and each assessment of reflexes will be summarized by study group and visit. The reflexes neurological examination of upper and lower extremities will be analyzed as continuous variables (0 = absent, 1 = trace, 2 = normal, 3 = brisk, 4 = clonus). The descriptive statistics will be summarized by study group and visit.

The motor neurological examination will be analyzed as continuous variable (0 = no contraction or can't position limb; 1 = flicker or trace contraction, no movement; 2 = movement only with gravity eliminated; 3 = movement against gravity; 4 = movement against gravity and resistance; 5 = normal strength). Summary statistics will be presented by study group and visit.

The Ashworth spasticity scale will also be analyzed as continuous variable (1 = normal; 2 = slight increase in tone; 3 = more marked increase in tone; 4 = considerable increase in tone; 5 = affected part rigid, immobile). Summary statistics will be presented by study group and visit.

The number and percentages of the status in each assessment of general neurological examination will be summarized by study group and visit. El Escorial data will be listed.

Baseline values will be taken from Day 1 pre-dose unless an entire section of the neurological exam (i.e. coordination/cerebellar function, reflexes, motor) is missing or not done, in which case for that specific section baseline will be taken from the Screening visit for all items within that section of the exam.

Listings will also be provided with complete details for the neurological examinations.

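### SAP 4.9.6 omits, without declaring it, the change-from-baseline summary that the protocol specifies for the limited neurological examination

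*Protocol*

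**What the plan says.** Protocol 16.6.2.5, in the current Version 6 text, is a single commitment: "The changes from baseline in the limited neurological examination (coordination/cerebellar function, reflexes, and motor system) will be summarized by visit".

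SAP 4.9.6 plans different outputs for the same examination:

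- Coordination and reflexes as categories: counts and percentages in each status, for each study group at each visit. The general neurological examination is treated the same way.
- Reflexes as a 0 to 4 score: "The descriptive statistics will be summarized by study group and visit".
- Motor strength on a 0 to 5 score: "The motor neurological examination will be analyzed as continuous variable". For this and for Ashworth spasticity, "Summary statistics will be presented by study group and visit".

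The section also sets a baseline rule: "Baseline values will be taken from Day 1 pre-dose unless an entire section of the neurological exam" is missing or not done, in which case that section's baseline comes from Screening. Full listings are planned.

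Neighbouring sections are worded differently. For ECG, SAP 4.9.4 says: "Summary statistics for actual values and change from baseline in each ECG parameter will be presented by study group and visit". For MMSE, SAP 4.9.5 says: "Summary statistics for actual values and change from baseline of the total score of MMSE will be presented for each visit by study group".

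**The concern.** A table of levels by visit measures change only if the same people are examined at each visit. That is unlikely here, in a progressive, fatal disease followed for up to 360 weeks, with an examination schedule that was cut back mid-study. Reading a later row against the baseline row mixes within-participant change with a change in who was examined. The protocol's statistic removes the second component. The SAP's tables do not, although the SAP defines the baseline needed to do so.

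At stake is one supporting safety summary for a drug given into the spinal canal, in a study whose primary objective is long-term safety and tolerability.

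**Working it through.** The documents state no figure on this point, so there is none to reproduce. The check has a textual part and an illustrative part.

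**1. Is the within-participant summary supplied anywhere in the SAP?**

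| Measure | SAP section | Comparison with own baseline |
|---|---|---|
| Laboratory data | 4.9.2 | Change from baseline and shifts |
| Vital signs | 4.9.3 | Change from baseline |
| ECG | 4.9.4 | Change from baseline and shifts |
| MMSE | 4.9.5 | Change from baseline |
| C-SSRS | 4.9.7 | New or worsening against baseline |
| Limited neurological examination | 4.9.6 | None; levels and status only |

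The general principles in SAP 4.1 list generic descriptive statistics and set no change-from-baseline default. SAP Section 5 declares two departures: efficacy and biomarker analyses moved to the integrated analysis, and the enriched/other subgroups dropped. This one is not declared.

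**2. Does the examined set change?**

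- SAP Section 1 links disease progression in Parts A and B to a large proportion of discontinuations, without giving a rate.
- Under Version 6 the examination is required only at Screening, Day 1 and the Final/Early Termination Visit. Elsewhere it is at the Investigator's discretion (Schedule of Activities, footnote 14; SAP Table 2).
- SAP 3.1 windows early-withdrawal and unscheduled examinations into scheduled-visit rows.
- SAP 4.9 excludes this examination from the missing-data summary.

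**3. Two-group illustration (all inputs assumed).** Motor score: 60% of participants start at 4.5 and 40% at 2.5. Everyone loses 0.50 and only weaker participants are lost.

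Baseline row = 0.6 × 4.5 + 0.4 × 2.5 = 3.70.

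Later row = (0.6 × 4.0 + r × 2.0) / (0.6 + r), where r is the weaker share still examined.

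| Weaker participants lost | r | Later row | Row difference | Paired change |
|---|---|---|---|---|
| 0% | 0.4 | 3.20 | -0.50 | -0.50 |
| 25% | 0.3 | 3.33 | -0.37 | -0.50 |
| 50% | 0.2 | 3.50 | -0.20 | -0.50 |
| 75% | 0.1 | 3.71 | +0.01 | -0.50 |

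The row difference reaches zero when 74% of the weaker group is lost (29% overall). For a decline of 0.25 the threshold is 43% (17% overall); for 0.75 it is 96% (38% overall). With a 30% weaker share and a decline of 0.75, reversal is impossible: even if only stronger participants remained, the later row would be 4.5 - 0.75 = 3.75, below the baseline row of 3.90.

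**4. The opposite direction.** With the same inputs, suppose all weaker participants but only half of the stronger are examined, as discretionary examination might produce. The later row is (0.3 × 4.0 + 0.4 × 2.0) / 0.7 = 2.86. The difference is -0.84, which overstates the true -0.50.

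**5. Simulations (all inputs assumed).**

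(a) N = 183, the maximum dosed in the parent study (Protocol 16.8); 4,000 runs; baseline normal with mean 3.5 and SD 1.0, held to 0 to 5; decline with mean 0.5 and SD 0.4. The logit of the loss probability is -0.6 + b × (follow-up score - 3.0). Overall loss is 35 to 43%.

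| b | Row difference | Paired change | Runs in which the level rises |
|---|---|---|---|
| 0 | -0.50 | -0.50 | 0% |
| -0.75 | -0.24 | -0.46 | under 0.1% |
| -1.5 | -0.05 | -0.44 | 24% |
| -2.5 | +0.09 | -0.42 | 90% |

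(b) Week 96; baseline mean 3.8 and SD 0.8; loss about 2% per 4 weeks, multiplied by exp(0.5 to 1.5) per point weaker; the same decline for everyone. Row differences are -0.05 to +0.22 for a true loss of 0.20, and -0.24 to +0.05 for 0.40. For 0.8 they are about -0.6 to -0.3, and for 1.2 about -1.0 to -0.6: attenuated, never reversed.

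**6. What paired change does not repair.** In step 3 it recovers the truth only because everyone declines equally. Let the stronger lose 0.3 and the weaker 0.8, so the true mean is 0.6 × 0.3 + 0.4 × 0.8 = 0.50. With 75% of the weaker lost, paired change is -(0.6 × 0.3 + 0.1 × 0.8) / 0.7 = -0.37, while the row difference is (0.6 × 4.2 + 0.1 × 1.7) / 0.7 - 3.70 = +0.14. Paired change keeps the sign but is attenuated.

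**The case against.** A reader might infer that the planned tables will hide or reverse neurological worsening and leave the primary safety question unanswered. The documents do not support that.

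- The primary endpoint is the incidence of AEs and SAEs and does not depend on these tables. The Version 3 amendment removed neurological examination abnormalities from that endpoint because clinically significant ones would be captured as AEs.
- SAP 4.9.1 tabulates AEs by preferred term and maximum grade, and treats serious neurologic events and falls as AEs of note with follow-up-adjusted rates. Full neurological listings are planned, so what is missing is a summary, not data.
- It is not established that each later row describes a fitter group. After Version 6 many examinations may be discretionary, which could favour participants with new complaints.
- Every size is assumed, and reversal disappears as the assumed decline grows.
- The baseline rule in SAP 4.9.6 suggests that change was intended and dropped out of the wording.

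All of this stands, and it limits the consequence. It does not close the gap: the SAP as written does not produce the protocol's summary, and a shift in the examined set in either direction makes levels a poor substitute for change.

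**Conclusion.** The mismatch is clear from the text and undeclared. The protocol specifies change from baseline by visit; the SAP delivers levels and status percentages and never uses its neurological baseline in a table.

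The consequence is conditional. Attenuation is plausible if weaker participants leave selectively. Reversal needs small declines with strong selective loss. Discretionary examinations could exaggerate decline instead. The documents give no motor score distribution, decline or loss rate, so the real size and direction cannot be computed, and nothing was quantified for coordination, reflexes or spasticity.

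The gap concerns a supporting safety summary. It should be corrected, but it does not threaten the primary endpoint, the neurologic AE summaries or the listings.

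**What to change.** In SAP 4.9.6:

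1. Add change from baseline for motor and Ashworth scores, by visit and at Final/Early Termination, in participants with both values. Show the paired n and those participants' baseline mean in the same row.
2. Add baseline-to-post-baseline shift tables for coordination/cerebellar function and reflexes, including Final/Early Termination. Reflexes need a shift table because 2 is normal and departures in both directions are abnormal, so means can cancel.
3. Derive the Final/Early Termination row separately from the visit windowing, which otherwise moves leavers' examinations into scheduled-visit rows.
4. Add a note that paired change is still attenuated if faster decliners leave, and that without a concurrent control it cannot separate a drug effect from disease progression.

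If the summary is to stay out, declare and justify this in SAP Section 5. The cost is SAP wording and a few tables from data already collected; no protocol amendment or new assessment is needed.

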16.6.2.6. Electrocardiogram

The changes from baseline will be summarized using shift tables. The number and percentage of participants with shifts to the categorical values (abnormal, not AE; or abnormal and AE) will also be summarized.

16.6.2.7. Antigenicity/Immunogenicity

Anti-BIIB067 antibody results will be summarized by prior treatment groups for participants from 233AS101 Part C and will also be summarized for participants from 233AS101 Parts A and B.

16.7. Interim Analyses

Interim analyses may be performed periodically to provide content for regulatory submissions and safety updates and to support drug development planning and business activities.

16.8. Sample Size Considerations

The sample size for this study is based on the number of the SOD1-ALS participants in Study 233AS101 who consent to participate. Up to 183 participants will be dosed in Study 233AS101.

CONFIDENTIAL

The information contained herein may not be used, disclosed, or published without the written consent of Biogen MA Inc.

17. ETHICAL REQUIREMENTS

The Sponsor and the Investigator must comply with all instructions, regulations, and agreements in this protocol and applicable ICH and GCP guidelines and conduct the study according to local regulations.

The Investigator may delegate responsibilities for study-related tasks where appropriate to individuals sufficiently qualified by education, training, and experience, in accordance with applicable ICH and GCP guidelines. The Investigator should maintain a list of the appropriately qualified persons to whom significant study-related duties have been delegated.

17.1. Declaration of Helsinki

This study will be performed in alignment with the ethical principles outlined in the Declaration of Helsinki.

17.2. Ethics Committee

The Investigator must obtain ethics committee approval of the protocol, ICF, and other required study documents prior to starting the study. The Sponsor will submit documents on behalf of the investigational sites.

If the Investigator makes any changes to the ICF, the Sponsor must approve the changes before the ICF is submitted to the ethics committee. A copy of the approved ICF must be provided to the Sponsor. After approval, the ICF must not be altered without the agreement of the relevant ethics committee and the Sponsor.

It is the responsibility of the Investigators to ensure that all aspects of institutional review are conducted in accordance with current applicable regulations.

Biogen must receive a letter documenting ethics committee approval, which specifically identifies the protocol, protocol number, and ICF, prior to the initiation of the study. Protocol amendments will be subject to the same requirements as the original protocol.

A progress report must be submitted to the ethics committee at required intervals and not less than annually.

At the completion or termination of the study, the investigational site must submit a close-out letter to the ethics committee and the Sponsor.

17.3. Participant Information and Consent

Prior to performing any study-related activities under this protocol, including screening tests and assessments, written informed consent with the approved ICF must be obtained from the participant or participant's legally authorized representative (e.g., spouse), as applicable, in accordance with local practice and regulations.

CONFIDENTIAL

The information contained herein may not be used, disclosed, or published without the written consent of Biogen MA Inc.

The background of the proposed study, the procedures, the benefits and risks of the study, and that study participation is voluntary for the participant must be explained to the participant (or the participant's legally authorized representative). The participant must be given sufficient time to consider whether to participate in the study.

Participants will be informed that their race and ethnicity will not be collected for the purposes of data analysis during the extension study. However, this information was collected in Study 233AS101, where applicable and after participant consent, unless the collection was not permitted by applicable law or not approved by the governing ethics committee, and the data will be used during analysis of the results of that study.

A copy of the signed and dated ICF must be given to the participant or the participant's legally authorized representative. The signed and dated ICF will be retained with the study records. Local regulations must be complied with in respect to the final disposition of the original (wet signature) and copies of the signed and dated ICFs.

Confirmation of informed consent must also be documented in the participant's medical record.

17.4. Participant Data Protection

Prior to any testing under this protocol, including screening tests and assessments, candidates must also provide all authorizations required by local law (e.g., PHI authorization in North America).

During the study, participants' race and ethnicity will not be collected for the purposes of data analysis.

Study reports will be used for research purposes only. The participant will not be identified by name in CRFs, study-related forms, study reports, or any related publications. The Sponsor, its partners and designees, ethics committees, and various government health agencies may inspect the records of this study. Every effort will be made to keep the participant's personal medical data confidential.

17.5. Compensation for Injury

The Sponsor maintains appropriate insurance coverage for clinical studies and will follow applicable local compensation laws.

17.6. Conflict of Interest

The Investigators should address any potential conflicts of interest (e.g., financial interest in the Sponsor or partnering companies) with the participant before the participant makes a decision to participate in the study.

CONFIDENTIAL

The information contained herein may not be used, disclosed, or published without the written consent of Biogen MA Inc.

17.7. Registration of Study and Disclosure of Study Results

The Sponsor will register the study and post study results regardless of outcome on a publicly accessible website in accordance with the applicable laws and regulations.

CONFIDENTIAL

The information contained herein may not be used, disclosed, or published without the written consent of
Biogen MA Inc.

18. ADMINISTRATIVE PROCEDURES

18.1. Study Site Initiation

The Investigator must not screen any participants prior to completion of a study initiation visit, conducted by the Sponsor or designee. This initiation visit will include a detailed review of the protocol and study procedures.

18.2. Quality Assurance

During and/or after completion of the study, quality assurance officers named by the Sponsor or the regulatory authorities may wish to perform onsite audits or inspections. The Investigator will be expected to cooperate with any audit or inspection and to provide assistance and documentation (including source data) as requested.

18.3. Monitoring of the Study

The Investigator must permit study-related monitoring by providing direct access to source data and to the participants' medical histories. Source data must be attributable, legible, contemporaneous, original, accurate, and complete. Changes to source data must be traceable, not obscure the original entry, and be explained if necessary (e.g., with an audit trail). The Investigator should maintain a record of the location(s) of essential documents.

The Clinical Monitor will visit the Investigator at regular intervals during the study and after the study has completed, as appropriate. During these visits, CRFs and supporting documentation related to the study will be reviewed and any discrepancies or omissions will be resolved.

Remote evaluation of data (centralized monitoring) and remote verification of source documentation may also be conducted and reported as defined in the Monitoring Plan.

Monitoring visits must be conducted according to the applicable ICH and GCP guidelines to ensure protocol adherence, quality of data, study treatment accountability, compliance with regulatory requirements, and continued adequacy of the investigational site and its facilities.

18.4. Study Funding

Biogen is the Sponsor of the study and is funding the study. All financial details are provided in the separate contracts between the institution, Investigator, and Biogen.

18.5. Publications

Details are included in the clinical trial agreement for this study.

CONFIDENTIAL

The information contained herein may not be used, disclosed, or published without the written consent of
Biogen MA Inc.

[figure not shown]
19. FURTHER REQUIREMENTS AND GENERAL INFORMATION

19.1. Public Health Emergencies

[figure not shown]
In the event of a public health emergency that results in site closure, travel restrictions, and/or the study being deprioritized at the site such that clinic visit(s) cannot occur, a protocol deviation would be incurred for any deviation from the protocol-specified visits and assessments, with additional notation that this protocol deviation is due to the public health emergency. If a protocol-specified clinical visit cannot occur because of a public health emergency, the following mitigating options should be pursued, in order of preference (in which the highest preference option that is feasible should be done): 1) transfer to another active study site that is open, 2) home visit, 3) telemedicine visit (e.g., by telephone or web conference), and 4) local laboratory visit. These mitigating options only apply in the setting of a public health emergency in which a protocol-specified clinic visit cannot occur and should not be pursued solely because of a participant's preference. If the participant does not participate in one of these options, a Safety Telephone call must be conducted within 14 days of the last dosing visit.

A third-party vendor has been engaged to perform the following assessments at the study participant's home:

- Limited neurological examination
- Physical examination
- Vital signs
- Height and body weight collection
- Health outcome measures

– C-SSRS

CONFIDENTIAL

The information contained herein may not be used, disclosed, or published without the written consent of
Biogen MA Inc.

- SVC
- Biological sample collection
- Pregnancy test (if applicable)
- HHD
- Collection/shipment of ventilation diary records

The following assessments will be performed via telephone (telemedicine) by the site staff:

- ALSFRS-R
- [REDACTED]
- Assessing changes in signs and symptoms as well as review of concomitant medications and AEs

